### **7.1.2 Independent Rater Screening Assessments**

If participants meet initial eligibility during Screening, a blinded IR will continue the eligibility assessment via telemedicine after reviewing the results of the LEC-5 and SCID-5-SPQ. The blinded IR interview may be recorded to assess reliability of ratings. The potential participant should be present at the study site during this assessment unless the study team has received permission for the participant to complete the assessment remotely. In either case, the therapy pair will be available for support. If a participant reports suicidal ideation during this assessment, the IR will contact the therapy pair after the call and present any concerns. The therapy pair is then required to follow-up with the participant to ensure safety, provide support, recommend treatment, or schedule a visit to the study site.

- Using the results of the SCID-5-SPQ to guide the interview, the IR will perform the SCID-5-PD to assess personality disorders. Only appropriate modules will be completed.
- The IR will also ask relevant questions from the DDIS to identify dissociative disorders and administer the Since Last Visit C-SSRS to determine suicidal risk.
- The IR will complete MINI interview to assess psychiatric disorders.

The results from the MINI, SCID-5-PD, DDIS, and C-SSRS will be provided to the therapy pair at the site to review along with all other Screening information to determine eligibility. Items assessed by the IR at this visit will be confirmed in the Preparatory Period by clinical observation, but the measures will not be repeated.

If the results of any interview indicate an exclusionary psychological disorder diagnosis is present, the Senior IR reviewer will review the recording of the MINI and/or SCID-5-PD assessment. The Senior IR reviewer will invite the study team (including therapists, site physician, and Clinical Investigator) to provide any additional information that may inform the Senior IR reviewer's opinion. The Senior IR reviewer will make the final judgment on whether or not the participant has an exclusionary diagnosis. Participants with exclusionary diagnoses

will not be enrolled. However, if any diagnosis is not present or uncertain according to any measure or interview, but the investigator believes the participant presents with a particular disorder, they may diagnose and deem the participant ineligible if appropriate.

After the initial screening visit the Irs will be blinded to visit number, treatment assignment, number of treatments received, and any study data for the participant. IR visits will be assigned based on availability.

### 7.1.3 Enrollment

In advance of Visit 0, the site team will review all notes from Screening visits, medical assessments, IR assessments, notes, discussions, medical records, and measures against eligibility criteria. The Sponsor will additionally perform eligibility review prior to enrollment at the site. If the participant is eligible, medication tapering and concomitant medications dose adjustments will be discussed, if applicable. The site physician will consult the prescribing physician to initiate medication tapering for participants. For all details on concomitant medications, tapering, allowed, and prohibited medications refer to [Section 11.0 Concomitant Medications](#).

At study onset, if a potential participant is eligible, the study team will contact the Medical Monitor and send a summary of the medical history for approval to enroll the potential participant. If a participant is determined to be eligible to participate in the study, the participant will be notified of enrollment at Visit 0. A medication tapering plan will be discussed with the participant, if applicable. Medical history and medication information will be reviewed for completeness. If agreeable, the participant will be enrolled in the study. Once enrolled, AE collection requirements begin (refer to [Section 10.0 Safety](#)). Visit 0 should take place within 2 to 14 days after Independent Rater Screening is completed. Visit 0 and Visit 1 may take place on the same day.

For eligible participants at Enrollment (Visit 0), qualified site staff will:

- Administer the MAPS-Adapted C-SSRS (Since Last Visit).
- Support participants in the completion of the following pre-treatment measures.
  - DRRI-II
  - ACE
  - OSU-TBI
  - UFEC
- Remind the participants of lifestyle modifications, including fasting and refraining from using psychoactive or non-approved medications, pertinent prior to the Experimental Session per [Section 3.3 Lifestyle Modifications](#).

## 7.2 Preparatory Period with Enrollment Confirmation

### 7.2.1 Preparatory Sessions

Participants will undergo three Preparatory Sessions (Visits 1, 2, and 4) lasting approximately 90 minutes with the therapy pair prior to the first Experimental Session. The Preparatory Period will be initiated within 12 days of Visit 0. There must be at least 48 hours between Preparatory Sessions 1 (Visit 1) and 2 (Visit 2) and 72 hours between the Baseline CAPS-5-T1 (Visit 3) and Preparatory Session 3 (Visit 4). The minimum time to complete the Preparatory Period is 7 days. Adherence criteria for Preparatory Sessions should be followed per the Treatment Manual. In these visits the therapy pair will work with the participant to prepare for MDMA-assisted therapy,

begin building therapeutic alliance, and promote a safe set and setting for confronting trauma-related memories, emotions, and thoughts.

Preparatory Sessions during the Preparatory Period will focus on psychoeducation about PTSD, building safety for the therapeutic relationship, developing the therapeutic alliance, obtaining the background for the trauma, and preparing the participant for the first Experimental Session.

- Preparatory Session 1 (Visit 1) will occur 0 to 12 days after Visit 0.
- Preparatory Session 2 (Visit 2) will occur at least 2 days after Visit 1 (depending on medication tapering).
- Preparatory Session 3 (Visit 4) will occur 3 to 6 days after the Baseline CAPS-5 (V3).

At each 90-minute psychoeducation and therapy Preparatory Session, the therapy pair will:

- Record the therapy session.
- Inquire about any possible changes in health to ensure the participant continues to meet all eligibility requirements. Record Aes as described in [Section 10.0 Safety](#).
- Inquire about concomitant medication use and adherence.
- Discuss goals and expectations for the Experimental Session, following standard procedures and techniques described in the Treatment Manual [\[111\]](#).

If a participant would like a companion present during or after the Experimental Session, a meeting between the therapy pair and that individual will be scheduled prior to the first Experimental Session. There must be mutual agreement between the participant and therapy pair concerning the presence of the companion.

At any time during the Preparatory Period, if a potential participant is deemed to be ineligible, the site team will classify them as a Pre-randomization Early Termination, notify the potential participant that they are not eligible for the study, and not schedule additional assessments. The site team will not randomize participants classified as Pre-randomization Early Terminations.

During one of the Preparatory Sessions, if possible, the therapy pair will introduce the participant to the attendant who will remain with the participant during each overnight stay after each MDMA-assisted therapy session. The attendant will be an individual with previous training in caregiving. The site will make all attempts to have the same attendant for each Experimental Session for a given participant, but it is not guaranteed.

### **7.2.2 Baseline CAPS-5 by Independent Rater**

At Baseline, an IR will measure the Baseline CAPS-5 (referred to as Baseline CAPS-5 T1) via telemedicine. This visit may be recorded to video to establish inter-rater reliability. The scores will be sent within 72 hours to the site staff. A CAPS-5 Total Severity Score of at least 28 is required to meet Enrollment Confirmation criteria. The IR will also administer the DSP-I and the SDS.

### **7.2.3 Baseline Self-Reported Measures**

Qualified site staff will administer the MAPS-Adapted C-SSRS (Since Last Visit) and actively support participants in the completion of the following self-reported measures. These measures should be completed after the Baseline CAPS-5 and before the Treatment Period begins.

- WHOQOL-BREF
- AAQ-II

- SCS
- BPAQ-SF
- PCL-5
- MIES
- BDI-II
- CPGS
- PTGI

#### **7.2.4 Enrollment Confirmation**

The Preparatory Period ends with Enrollment Confirmation. A participant's enrollment will be confirmed if they have completed medication tapering, have a confirmed PTSD diagnosis per the CAPS-5 assessment with a Total Severity Score of 28 or greater, a total PCL-5 score of 36 or greater at Screening, continue to agree to all lifestyle modifications, and continue to meet all eligibility criteria.

### **7.3 Treatment Period**

#### **7.3.1 Experimental Sessions**

There will be two or three Experimental Sessions, depending on group (Visits 5 and 9 for 2-session group; Visits 5, 9, and 13 for 3-session group). Procedures for MDMA-assisted therapy will remain the same across all sessions and all procedures regardless of assigned group. Experimental Sessions must be at least 6 to 8 hours long, measured from 30 minutes prior to IMP administration.

- Experimental Session 1 (Visit 5) will occur within 7 days after Preparatory Session 3 (Visit 4). If the Baseline CAPS-5 assessment is completed outside of the allowed window, the investigator should consult the CRA and Medical Monitor to determine if the assessment should be repeated. The first Experimental Session will include an initial dose of 120 mg of MDMA followed by a supplemental dose of 40 mg 1.5 to 2 hours after the initial dose unless tolerability issues emerge with the first dose or it is refused by the participant.
- Experimental Session 2 (Visit 9) will occur 21 to 35 days after Experimental Session 1 (Visit 5). An initial dose of 120 mg MDMA will be administered. A supplemental dose of 40 mg will be administered 1.5 to 2 hours after the initial dose unless tolerability issues emerge with the first dose or it is refused by the participant.
- Group 1 only: Experimental Session 3 (Visit 13) will occur 21 to 35 days after the second Experimental Session (Visit 9). An initial dose of 120 mg will be administered. A supplemental dose of 40 mg will be administered 1.5 to 2 hours after the initial dose unless tolerability issues emerge with the first dose or it is refused by the participant.

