**Table 1: CAPS-5 Data Collection by Visit**

CAPS Number	Visit	Description/Timing	Target Timing Post Baseline
Baseline CAPS-5 T1	V3	Baseline between Visits 2 and 4 (Preparatory Sessions), after medications have been tapered.	Not Applicable
CAPS-5 T2	V13 (2-session group) or V17 (3-session group)	Post Treatment Primary Outcome 49 to 56 days after last Experimental Session	63 to 98 days or 85 to 134 days
CAPS-5 T2.2	V15 (2-session group only)	Secondary outcome for 2-session group only 28 to 35 days after T2	85 to 134 days

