#### **4.3 Planned Duration of Study**

Full screening may take 28 days after completion of initial screening. The Preparatory Period begins at enrollment and can be as brief as 7 days but depending on medication tapering could be as long as necessary to ensure an appropriate medication washout of at least five half-lives of pre-study psychiatric medications and active metabolites, and at least 7 days for stabilization prior to Baseline CAPS-5 T1 (Visit 3). Medication taper for psychological medications should occur prior to Visit 3. Medication taper for medications with drug-drug interactions without a psychological concern should occur prior to Visit 5.

Enrollment confirmation takes place at the completion of the Preparatory Period; at which time the Treatment period will commence. Participant eligibility must be confirmed by the Medical Monitor prior to participant randomization. Treatment begins within 7 days of Baseline CAPS-5 T1 (Visit 3).

The approximately 6 to 15-week treatment period consists of two or three Experimental Sessions 3 to 5 weeks apart with associated non-drug Integrative Sessions. The protocol may remain active up to enrollment of 60 participants. All participants who complete the study will be asked to participate in a LTFU extension study at least 6 months after the last Experimental Session.

After the final Integrative Session 3.3 (Visit 16) or 2.3 (Visit 12) (for the 3 Experimental Session Group and 2 Experimental Session Group, respectively), participants will enter follow-up with no planned study visits for approximately 4 weeks, after which the Primary Outcome CAPS-5 T2 assessment will take place. Participants in the 2-session group will complete an additional CAPS 5 T2.2 assessment after 4 more weeks. Although there are allowable windows for all visits throughout the protocol, the overall timelines should comply with the target timing of the Primary Outcome CAPS-5 T2 assessment, which must be completed 85 to 134 days post Baseline (3-Session Group) and 63 to 98 days post Baseline (2-Session Group), even if the maximum possible visit windows were used between visits. Other visits should be scheduled to ensure the timing of the Primary Outcome CAPS-5 T2 assessment is appropriate. The Study Termination visit occurs after the final CAPS-5 assessment.

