**Table 5: Treatment Period, Follow-Up, and Study Termination-Group 1 (3 Experimental Sessions)**

	Treatment Period: Group 1 (3 Experimental Sessions) ~9-15 weeks												Post-Treatment Period (~5 weeks)		
	Treatment 1				Treatment 2				Treatment 3				Primary Outcome	Outcome Site Visit	Study Termination
Visit	V5	V6	V7	V8	V9	V10	V11	V12	V13	V14	V15	V16	V17	V18	V19
Visit Description	Exp.1	Int. 1.1	Int. 1.2	Int. 1.3	Exp. 2	Int. 2.1	Int. 2.2	Int. 2.3	Exp. 3	Int. 3.1	Int. 3.2	Int. 3.3	CAPS-5 T2 Outcome: Telemedicine A	Outcome Site Visit	Study Termination
Visit Timing	Within 7 days after V3	Morn-ing after V5	~1 week (3 to 14 days) after V5	~2 weeks (10 to 21 days) after V5	~3 weeks (21 to 35 days) after V5	Morn-ing after V9	~1 week (3 to 14 days) after V9	~2 weeks (10 to 21 days) after V9	~3 weeks (21 to 35 days) after V9	Morn-ing after V13	~1 week (3 to 14 days) after V13	~2 weeks (10 to 21 days) after V13	85 to 134 days after V3; ~ 7 weeks after V13	2 days (1 to 7 days) after V17	~2 days (0 to 7 days) after V18
Past/Current Medication & Adherence	S #	S #	S #	S #	S #	S #	S #	S #	S #	S #	S #	S #		S #	S #
Drug Screen	S #				S #				S #						
Pregnancy Screen B	S #				S #				S #						
Biomarker Blood Sample													S C		
Record	S #	S #	S #	S #	S #	S #	S #	S #	S #	S #	S #	S #	S #		
All AEs D	S #	S #	S #	S #	S #	S #	S #	S #	S #	S #	S #	S #		S #	S #
Randomization E	S #														
Administer IMP	S #				S #				S #						
8-hour Exp. Session	S #				S #				S #						
BP, Pulse, Temp. F	S #				S #				S #						S G
Overnight Stay	S #				S #				S #						
90-min Integrative Session		S #	S #	S #		S #	S #	S #		S #	S #	S #			
Phone Call Follow-up H		S #				S #				S #					
Weight													#	S #	

A All visits must be scheduled to ensure that the Primary Outcome CAPS-5 T2 assessment is within the overall window provided.

B For people able to become pregnant (PAPB) only

C Blood samples will be drawn from participants at two time points (pre- and post-treatment) in order to bank samples for future assay.

D All Adverse Events (AEs) includes collecting Serious Adverse Events, Aes of Special Interest, Aes of Psychiatric Status, Aes requiring medical advice or attention, Aes that indicate withdrawal of a participant, and all other Aes

E Randomize 24 to 48 hours prior to first Experimental Session

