**Table 6: Treatment Period, Follow-Up, and Study Termination-Group 2 (2 Experimental Sessions)**

	Treatment Period: Group 2 (2 Experimental Sessions) ~6-10 weeks								Post-Treatment Period (~9 weeks)			
	Treatment 1				Treatment 2				Primary Outcome	Outcome Site Visit	Secondary Outcome	Study Termination
Visit	V5	V6	V7	V8	V9	V10	V11	V12	V13	V14	V15	V16
Visit Description	Exp. 1	Int. 1.1	Int. 1.2	Int. 1.3 G	Exp. 2	Int. 2.1	Int. 2.2	Int. 2.3	CAPS-5 T2 Outcome: Tele-medicine A	Outcome Site Visit	CAPS-5 T2.2 Outcome: Tele-medicine	Study Termination
Visit Timing	Within 7 days after V3	Morning after V5	~1 week (3 to 14 days) after V5	~2 weeks (10 to 21 days) after V5	~3 weeks (21 to 35 days) after V5	Morning after V9	~1 week (3 to 14 days) after V9	~2 weeks (10 to 21 days) after V9	63 to 98 days after V3; ~ 7 weeks after V9	2 days (1 to 7 days) after V13	85 to 134 days after V3	~2 days (1 to 7 days) post V15
Past/Current Medication & Adherence	S #	S #	S #	S #	S #	S #	S #	S #		S #	S #	S #
Drug Screen	S #				S #							
Pregnancy Screen B	S #				S #							
Biomarker Blood Sample									S C			
Record	S #	S #	S #	S #	S #	S #	S #	S #	S #			
All Aes D	S #	S #	S #	S #	S #	S #	S #	S #		S #	S #	S #
Randomization E	S #											
Administer IMP	S #				S #							
8-hour Exp.Session	S #				S #							
BP, Pulse, Temperature F	S #				S #							S G
Overnight Stay	S #				S #							
90-min IntegrativeSession		S #	S #	S #		S #	S #	S #				
Phone Call Follow-up H		S #				S #						
Weight												S #

A All visits must be scheduled to ensure that the Primary Outcome CAPS-5 T2 assessment is within the overall window provided.

B For people able to become pregnant (PAPB) only

C Blood samples will be drawn from participants at two time points (pre- and post-treatment) in order to bank samples for future assay. Post-treatment blood draw will occur within 9 days of V13.

D All Adverse Events (Aes) includes collecting Serious Adverse Events, Aes of Special Interest, Aes of Psychiatric Status, Aes requiring medical advice or attention, Aes that indicate withdrawal of a participant, and all other Aes

E Randomize 24 to 48 hours prior to first Experimental Session

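### Section 7.3.1 counts the first-dose window from Visit 4, while Section 4.3 and Tables 5 and 6 count it from Visit 3, so the latest allowed first dose is day 13 or day 7 after baseline

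*Protocol*

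**What the plan says.** The protocol times the first Experimental Session (Visit 5) in two ways.

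- **Counted from Visit 4.** Section 7.3.1: "Experimental Session 1 (Visit 5) will occur within 7 days after Preparatory Session 3 (Visit 4".
- **Counted from Visit 3.** Section 4.3: "Treatment begins within 7 days of Baseline CAPS-5 T1 (Visit 3". The Visit Timing rows of Tables 5 and 6 agree, with the entry "Within 7 days after V3".

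Section 7.2.1 links the two visits: "Preparatory Session 3 (Visit 4) will occur 3 to 6 days after the Baseline CAPS-5 (V3". Table 4 gives the same interval.

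Table 1 sets the window for T2, counted from baseline, at "63 to 98 days or 85 to 134 days" for the 2-session and 3-session groups respectively. Section 4.3 requires T2 to meet these limits "even if the maximum possible visit windows were used between visits". Footnote A to Tables 5 and 6 adds: "All visits must be scheduled to ensure that the Primary Outcome CAPS-5 T2 assessment is within the overall window provided".

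The sentence in Section 7.3.1 that follows the Visit 5 rule begins: "If the Baseline CAPS-5 assessment is completed outside of the allowed window, the investigator should consult the CRA and Medical Monitor". They are to decide whether the assessment should be repeated. The SAP gives no window for Visit 5.

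**The concern.** Both rules set a seven-day upper limit, but from starting points 3 to 6 days apart. A first dose on days 8 to 13 after the Baseline CAPS-5 can therefore comply with Section 7.3.1 and breach Section 4.3 and Tables 5 and 6.

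Two practical decisions depend on which rule applies. One is the consultation on repeating the baseline, if its undefined window means the interval from baseline to first dose, which is the natural reading in that place. The other is deviation recording: Section 4.3 asks for delays outside protocol windows to be documented as deviations where appropriate, and SAP Section 7.3 still tabulates deviations as major or minor. The age of the baseline at first dose also varies with the rule, and SAP Section 7.7.1 still reports CAPS-5 change from baseline with 95% confidence intervals.

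Endpoint validity is not at stake, since no analysis set in either document has a timing condition.

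**Working it through.** Days are counted from Visit 3 (Baseline CAPS-5 T1 = day 0).

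**Inputs**

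| Input | Value | Source |
|---|---|---|
| Visit 4 | days 3 to 6 | Section 7.2.1, Table 4 |
| Visit 5, Visit 3 rule | by day 7 | Section 4.3, Tables 5 and 6 |
| Visit 5, Visit 4 rule | up to 7 days after Visit 4 | Section 7.3.1 |
| Interval between Experimental Sessions | 21 to 35 days | Section 7.3.1 |
| Last session to T2 | 49 to 56 days | Table 1 |
| T2 upper limit | day 98 (2-session), day 134 (3-session) | Section 4.3, Table 1 |

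**Step 1. Reproduce the plan's T2 limits.** Latest T2 = latest Visit 5 + 35 (+ 35 more for three sessions) + 56. With Visit 5 on day 7:

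- 2-session: 7 + 35 + 56 = 98, equal to the limit.
- 3-session: 7 + 35 + 35 + 56 = 133, one day inside the limit of 134.

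The stated limits are consistent with the Visit 3 rule.

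**Step 2. Apply the Section 7.3.1 rule.** Latest Visit 5 = 6 + 7 = day 13. Then:

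- 2-session: 13 + 35 + 56 = 104, which is 6 days over.
- 3-session: 13 + 35 + 35 + 56 = 139, which is 5 days over.

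**Step 3. Solve for the latest Visit 5 that keeps T2 in window at maximum windows.** 98 − 35 − 56 = day 7 for two sessions; 134 − 70 − 56 = day 8 for three. Day 13 meets neither.

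**Step 4. Check whether T2 is forced out.** With Visit 5 on day 13 and 35-day spacing, the earliest T2 is 13 + 35 + 49 = 97 or 13 + 35 + 35 + 49 = 132. Both are in window, but with little room:

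| Visit 5 | 2-session: T2 days in window | 3-session: T2 days in window |
|---|---|---|
| day 7 | 91 to 98 (8 of 8) | 126 to 133 (8 of 8) |
| day 13 | 97 to 98 (2 of 8) | 132 to 134 (3 of 8) |

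**Step 5. Count the schedules on which the rules disagree.** With Visit 5 from 1 to 7 days after Visit 4, Section 7.3.1 permits 4 × 7 = 28 whole-day combinations. Visit 5 falls after day 7 in 3, 4, 5 and 6 of them for Visit 4 on days 3, 4, 5 and 6, a total of 18. If a same-day Visit 4 and Visit 5 is also counted, it is 18 of 4 × 8 = 32; randomization 24 to 48 hours before dosing makes 28 the more realistic base. These are counts of possible schedules, not expected proportions of participants.

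**The case against.** The strongest reply is that the two rules can both be met. Each is an upper limit, a first dose by day 7 satisfies both, and a site that reads the whole protocol would follow the tighter one, which appears in three places. T2 is protected separately by Section 4.3 and footnote A, so days 104 and 139 arise only if a site uses every maximum window and ignores those instructions. SAP Section 7.3 has a committee judge each deviation by its impact, so major or minor status does not follow mechanically from the anchor. Section 7.0 already requires the CRA to be told of delays and deviations. With the study stopped early, a changed dosing window may alter no participant's schedule.

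Most of this stands, and it keeps the point small. It does not remove the contradiction. Section 7.3.1 is the section that describes how the sessions are run, and a site following it in good faith could dose on days 8 to 13. Nothing states that the tighter limit prevails. The committee must first know whether a deviation occurred before it can grade it.

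The Visit 3 rule is also tight, and this is a fair caution about the remedy. With Visit 4 on day 6, only day 7 remains for dosing. Enrollment confirmation, the Medical Monitor's confirmation and randomization at least 24 hours ahead would then all crowd into the end of that interval. It is feasible but leaves no slack.

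**Conclusion.** The inconsistency is real. The latest permitted first dose is day 13 under Section 7.3.1 and day 7 under Section 4.3 and Tables 5 and 6, a gap of 6 days. Section 7.3.1 is the text to correct: the other three places agree with each other, and only the Visit 3 rule satisfies the maximum-window condition on T2.

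The consequence is limited to how recent the baseline is and how deviations are classified. Power, the analysis sets and the validity of T2 are unaffected, and with about 20 participants and no primary efficacy analysis the practical impact is small. The correction should still be made, because this is an operative dosing rule and the change costs almost nothing.

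The day counts assume whole days from Visit 3. The repeat-baseline consequence assumes that the undefined window in Section 7.3.1 is the interval from baseline to first dose.

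**What to change.** In Section 7.3.1, change the anchor for Experimental Session 1 from Preparatory Session 3 (Visit 4) to the Baseline CAPS-5 T1 (Visit 3), keeping the seven-day limit. Apply the same rule to the repeat-baseline decision and to deviation classification under SAP Section 7.3. If dosing is already complete, the last of these is the part that still matters.

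Tell sites that a Visit 4 on day 6 leaves only day 7 for Visit 5, so an earlier Visit 4 is preferable.

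The cost is one phrase in one sentence. No procedure is added, and the T2 and T2.2 limits stay as they are: under the Visit 3 rule the latest T2.2 is 98 + 35 = day 133, inside its limit of 134.
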